T: [contact] [name]
Email: [contact]

[figure not shown]
Participating non-COH sites**Site PI**

[name]
University of Nebraska
[name]
[name]
T: [contact]
Email: [contact]

Site PI

[name]
Winship Cancer Institute of
Emory University
[name]
[name]
T: [contact]
Email:
[contact]

EXPERIMENTAL DESIGN SCHEMA

Each cycle = 21 days. Maximum duration of protocol therapy is 24 months.

Folic acid and Vitamin B12 supplementation is standard of care for pralatrexate therapy.

Folic acid is given daily during the course of therapy. Vitamin B12 is given every 3 cycles.

¹ Disease staging is performed at screening and every 4 cycles until disease progression or off study therapy. Disease staging will be by either PET/CT (preferred) or CT scan, but, if disease is FDG-avid, will be PET/CT at baseline, Cycle 4 and every 8 cycles thereafter. Refer to [Study calendar](#) and [Section 11.1](#) for details.

² Peripheral blood for correlative studies will be collected on C1D1, C2D1, C4D1, C5D1, and at EOT (refer to [Table 9.3.1](#) for additional details).

³ End of treatment visit.

⁴ Follow-up Phase for patients who have completed treatment without disease progression will include staging every 12 weeks for the first year and every 18 weeks thereafter, until disease progression or off study.

PROTOCOL SYNOPSIS

Protocol Title	
A Phase 1/2 Study of Pembrolizumab plus Pralatrexate for Treatment of Relapsed or Refractory Peripheral T-cell Lymphomas	
Study Detail	
Population/Indication(s):	Relapsed/Refractory Peripheral T-cell Lymphomas
Phase:	1/2
Sample Size:	Expected: 30 evaluable (Phase 1: 12 evaluable, Phase 2: 24 evaluable (including up to 6 patients from Phase 1 at RP2D) Maximum: 40
Estimated Accrual Duration:	48 months
Estimated Study Duration	6 years
Participant Duration:	Until progression, unacceptable toxicity, or withdrawal
Participating Sites:	
 • City of Hope Duarte, CA • University of Nebraska, NE • Emory University, GA
Study Agents:	Pembrolizumab, Pralatrexate
Sponsor:	City of Hope
Industry Partner:	Merck, Acrotech Biopharma, LLC
Rationale for this Study	

Outcomes of patients with relapsed or refractory PTCL are dismal. Current therapies available for relapsed or refractory PTCL, including novel agents, are associated with poor response rates and short median progression-free survival, and few patients are salvaged by stem cell transplantation.¹⁻⁵ Novel therapies for relapsed or refractory PTCL are urgently needed. Because of inadequate response rates using novel therapies as single agents in PTCL, we anticipate that novel therapeutic combinations will be necessary to impact these aggressive and difficult-to-treat diseases.
 
In early studies evaluating PD-1/PD-L1 pathway inhibitors in PTCL and MF/CTCL, response rates of 15-40% have been observed. Therefore, these well-tolerated immunotherapy agents with a different mechanism of action compared to all other available drugs for treating T-cell lymphomas are a potential backbone on which to build a novel therapy combination. One logical combination partner for a PD-1/PD-L1 inhibitor in PTCL is the antifolate drug, pralatrexate. Antifolate agents, like pemetrexed, have immunologic effects which may result in synergy with PD-1 blockade, including activation of IFNγ-producing NK cells and, potentially, activation of CD8+ T-cells.^{6,7} There is already clinical evidence of potential synergy between PD-1 inhibitors and anti-folate drugs. In a randomized phase II trial of patients with metastatic non-small cell lung cancer (NSCLC), patients treated with a PD-1 inhibitor, pembrolizumab, plus with carboplatin and an antifolate chemotherapy, pemetrexed, had a higher ORR (71%) than patients treated with pembrolizumab combined with carboplatin and paclitaxel (ORR 50%). (Gadgeel, ASCO 2015; Papadimitrakopoulou, ASCO 2014). We propose a phase 1/2 study to evaluate the safety and efficacy of combining pralatrexate with pembrolizumab for the treatment of relapsed or refractory aggressive PTCL.
	
Objectives	

Primary Objective
 
 ○ Evaluate the safety and tolerability of a regimen combining pembrolizumab and pralatrexate in patients with relapsed or refractory PTCL. ○ Establish the maximum tolerated dose (MTD) and recommended phase II dose (RP2D) of the combined pralatrexate and pembrolizumab regimen. ○ Estimate the overall response rate (ORR) according to the Lugano Classification⁸ in patients treated with 	

pembrolizumab plus pralatrexate at the RP2D.

Secondary Objective

- Estimate the complete response (CR) rate according to the Lugano Classification,⁸ duration of response (DOR), overall survival (OS) and progression-free survival (PFS) in patients treated with pembrolizumab plus pralatrexate.
- Estimate the ORR and CR rate according to the International Harmonization Project response criteria (Cheson 2007).⁹
- Evaluate responses and disease progression according to the Lymphoma Response to Immunomodulatory therapy Criteria (LYRIC).¹⁰

Exploratory Objective

- Explore immunologic and genomic biomarkers of response to pembrolizumab plus pralatrexate therapy.

Study Design

This is a prospective, single-arm, multi-center, open-label phase 1/2 study of pembrolizumab (MK-3475) plus pralatrexate in subjects with relapsed or refractory peripheral T-cell lymphomas (PTCL) that have failed at least one prior line of therapy.

The phase 1 dose-escalation portion of the study, with 2 dose levels and 1 possible de-escalation dose level, will determine the MTD and RP2D of the combination therapy. The starting dose will be 20 mg/m² of pralatrexate on days 1 and 8 and 200 mg IV of pembrolizumab every 21 days, administered in 21-day cycles. The planned dose levels in the Phase 1 portion of the study are outlined in the table below. The phase 1 portion will use a modified rolling 6 design allowing 3 patients to be treated and evaluated for dose-limiting toxicity simultaneously, with up to 6 patients per dose level.

Dosing regimen and schedule

Dose level	Pembrolizumab (Day 1)	Pralatrexate (Days 1 and 8)
-1	200 mg IV	15 mg/m ² IV
1	200 mg IV	20 mg/m ² IV
2	200 mg IV	30 mg/m ² IV

In the phase 2 portion, pembrolizumab will be administered at a dose of 200 mg IV and pralatrexate at the RP2D selected in the phase 1 portion following the same schedule. The phase 2 portion will use a Gehan two-stage design with advancement to the second stage based on ORR in the first stage.

In both phases, patients will receive up to 24 months of combined pembrolizumab and pralatrexate therapy. In both phases, Vitamin B12, Folic acid and Leucovorin will be administered as indicated in the study calendar and [Section 5.13.2](#).

Evaluation Criteria and Endpoints

Response/progression

Disease response/progression will be evaluated using 2014 Lugano Classification^{8,11}. Participants who meet the definition of progressive disease per Lugano Classification⁸ should be evaluated using the LYRIC criteria¹⁰. The ORR and CR rate will also be estimated according to the International Harmonization Project response criteria (Cheson 2007).⁹

Primary Endpoints

- Dose limiting toxicity (DLT) (defined in [Section 5.5](#)). The DLT observation period will be 2 cycles. Toxicities will be graded according to the National Cancer Institute Common Terminology Criteria for Adverse Events (CTCAE, Version 5.0).
- Overall response rate (ORR), per the Lugano classification.⁸

Secondary Endpoints

- Complete Response (CR) rate per the Lugano classification.⁸
- ORR and CR rate according to the International Harmonization Project response criteria (Cheson 2007).⁹
- Duration of Response (DOR).
- Overall Survival (OS).
- Progression-Free Survival (PFS).
- Toxicity: Toxicity and adverse events will be recorded using the NCI CTCAE 5.0 scale. Observed toxicities will be summarized by type (organ affected or laboratory determination such as absolute neutrophil count), severity (by NCI CTCAE v5.0 and nadir or maximum values for lab measures), date of onset, duration, reversibility, and attribution.
- Unacceptable Toxicity (defined in [Section 11.2](#))

Statistical Considerations

Phase 1 portion

During the Phase 1 portion of the study, a modified, more conservative version of the Rolling 6 design of Skolnik et al will be employed. In this design, at most, 3 patients will be under observation for DLT on the current test dose level at any time. DLT observation period is 2 cycles. Patients who did not receive the doses of pembrolizumab during DLT period (not due to DLT), or those who missed any doses of pralatrexate during DLT period (not due to DLT) will be replaced. Once 3 patients are evaluable with no patient at that dose level experiencing a DLT, the dose can be escalated, or up to 3 additional patients may be treated at the current dose level. No more than 6 evaluable patients will be accrued to any dose level. Escalation will terminate as soon as \geq 2 patients experience DLT at a given dose level. If 1/6 patients experience DLT at the current dose level, the dose will be escalated to the next higher level. If more than 1/6 patients experience DLT, then the next lower dose will be expanded. MTD will be declared the highest dose level at which 6 evaluable patients have been treated and, at most, 1/6 patients experiences DLT. The MTD will be considered the RP2D, unless the PI chooses a lower dose level, based on toxicity in subsequent cycles.

Phase 2 portion

In the phase 2 portion, patients will be treated at the RP2D. The phase 2 portion of this study will implement a Gehan two-stage design to estimate the ORR and to evaluate the activity of the combined regimen. Patients treated during the Phase 1 portion at the RP2D will be included in the Phase 2 evaluations if they are evaluable for response, defined as patients who received at least 1 dose of pembrolizumab and at least 1 dose of pralatrexate and had at least 1 disease assessment. The sample size is based on the desire to estimate the response rate with approximately 10% standard error, and early stopping if the combination is unexpectedly ineffective. In the pivotal PROPEL trial, the overall response rate (ORR) in 109 evaluable patients who received pralatrexate as a single agent was 29%, including 12 (11%) complete responses (CR) and 20 (18%) partial responses (PR).⁵

The phase 2 portion of the study is expected to evaluate a minimum of 7 and a maximum of 24 patients evaluable for response, including the patients treated at RP2D during the Phase 1 portion. At stage 1, if 0 responses are seen in the first 7 patients (including up to 6 patients enrolled during the Phase 1 portion that are evaluable for response), the study will be terminated and the true ORR will be declared $\leq 35\%$. If at least 1 patient responds, the trial will continue to the second stage. At stage 2, a total of 24 patients will be evaluated (including up to 6 patients enrolled during the Phase 1 portion that are evaluable for response).

This design provides for estimation of the response rate with approximately 10% standard error. The standard error will be 9.4%-10.2% after 24 patients if the ORR rate is 30%-70%. Under this design if the ORR is $> 35\%$, there would be $\geq 95\%$ chance of at least one response among the first 7 patients.

Safety Analysis and Stopping Rules for Excessive Toxicity or Rapid Disease Progression

Because of the unique immune-related adverse events (IrAEs) observed with checkpoint inhibitors, we will monitor for "Unacceptable toxicity" (defined in [Section 11.2](#)) and treatment-related mortality at any time during study treatment with this new combination of drugs. This monitoring will include all patients treated on the study regardless of the dose levels they were on. The expected rate of "unacceptable toxicity" should not be $> 33\%$. If the rate of "unacceptable toxicity" is $> 33\%$ after at least 6 patients are treated on study at any bi-annual safety review, or if a 2nd death that is at least possibly related to study treatment occurs regardless of the number of patients on study, accrual will be halted and a full review of these events will be performed by the City of Hope Data Safety Monitoring Committee (DSMC). Patient accrual will not resume until approved by the DSMC to do so. These rules are in addition to the bi-annual review of all toxicities submitted to the City of Hope Data Safety Monitoring Committee (DSMC). Patients with ongoing toxicity will be followed until resolution or stability.

In addition, because of the evidence that PD-1 may act as a tumor suppressor in preclinical T-cell lymphoma models and the recent reports of rapid disease progression in patients with ATLL, a subtype of PTCL, we will also monitor for rapid progression of disease. If at any bi-annual safety review during the conduct of the study, and after at least 3 patients are treated on study, $> 33\%$ of patients who received at least one dose each of pembrolizumab and pralatrexate experience rapid progression, the study accrual will be halted and a full review of these events will be performed by the City of Hope Data Safety Monitoring Committee (DSMC). Patient accrual will not resume until approved by the DSMC to do so.

Abbreviated Eligibility Criteria

Main Inclusion Criteria

- Age 18 or older
- ECOG performance status of 0 or 1.
- Patients must have a histologically confirmed diagnosis of mature peripheral T-cell or NK-cell lymphoma according to the WHO classification, including transformed mycosis fungoides, with hematopathology review at the participating institution. Refer to [Section 3.1](#) for a full list of eligible histologies.
- Patients must have failed at least one prior regimen.
- Patient must have measurable disease by CT or PET scan, with one or more sites of disease $\geq 1.5\text{cm}$ in longest dimension.
- Be willing to provide tissue from a fresh core or excisional biopsy (performed as standard of care) of a tumor lesion prior to starting study therapy or from archival tissue of a biopsy that was performed after the most recent systemic therapy. Exception can be granted by the PI if a biopsy is not feasible and/or safe.
- Patients must have received one dose of Vitamin B12 (1 mg IM) within 10 weeks prior to first dose of

pralatrexate, and must have begun folic acid supplementation (1 mg orally, once daily) within 10 days of first dose of pralatrexate. Note: if folic acid was not started but MMA and HCY levels were checked and are in normal range at screening, the investigator can decide to start study therapy immediately. Vitamin B12 and folic acid supplementation is standard of care for pralatrexate therapy.

- Adequate hematological, renal, and hepatic function.
- Female of childbearing potential: negative urine or serum pregnancy test within 72 hours prior to receiving the first dose of study medication.
- Agreement to use effective methods of contraception for both women of childbearing potential and male patients during the study and through 6 months post-last dose of pralatrexate for women and 3 months post-last dose of pralatrexate for man, and 120 days post-last dose of pembrolizumab for both women and men.

Main Exclusion Criteria

- Patients with adult T-cell leukemia/lymphoma.

Prior Therapy and Concomitant Therapy

- Prior allogeneic hematopoietic stem cell transplantation within the last 5 years.
- Prior autologous hematopoietic stem cell transplant within the last 60 days.
- Patients who received prior therapy with an anti-PD-1, anti-PD-L1, or anti-PD-L2 agent without having had evidence of objective response.
- Patients who received prior therapy with pralatrexate without having had evidence of objective response.
- Investigational agent or anti-cancer monoclonal antibody (mAb) within 21 days prior to Day 1 of therapy or who has not recovered (i.e. ≤ 1 or at baseline) from adverse events due to agents administered more than 21 days earlier.
- Prior chemotherapy, targeted small molecule therapy, or radiation therapy within 14 days prior to Day 1 of therapy or who has not recovered (i.e. ≤ 1 or at baseline) from adverse events due to a previously administered agent. Note: Subjects with \leq Grade 2 neuropathy are an exception and may qualify for the study.
- Antineoplastic biologic therapy or major surgery within 21 days of the first dose of trial medication. If subjects received major surgery more than 21 days ago, they must have recovered adequately from the toxicity and/or complications from the intervention prior to starting therapy.
- Received live vaccine or live-attenuated vaccine within 30 days prior to Day 1 of protocol therapy. Administration of killed vaccines is allowed.
- Systemic steroid therapy or on any other form of immunosuppressive therapy within 7 days prior to the first dose of trial treatment.

Other Illnesses and Conditions

- Diagnosis of immunodeficiency.
- Has a known additional malignancy that is progressing or requires active treatment. Exceptions include basal cell carcinoma of the skin or squamous cell carcinoma of the skin that has undergone potentially curative therapy or in situ cervical cancer.

- Congestive heart failure Class III/IV according to the New York Heart Association (NYHA) Functional Classification.
- Known severe hypersensitivity reaction to pembrolizumab, pralatrexate, leucovorin or any excipients.
- Active autoimmune disease that has required systemic treatment in the past 2 years (replacement therapies for hormone deficiencies are allowed). Hemolytic anemia associated with the lymphoma does not exclude a patient from the study.
- Known history of HIV (HIV \geq antibodies).
- Known active Hepatitis B (e.g., HBsAg reactive) or Hepatitis C (e.g., HCV RNA [qualitative] is detected).
- History of active TB infection (Bacillus Tuberculosis).
- Active central nervous system (CNS) involvement by lymphoma, including parenchymal and/or lymphomatous meningitis.
- Has a history of (non-infectious) pneumonitis/interstitial lung disease that required steroids or current pneumonitis/interstitial lung disease
- Active, uncontrolled infection requiring systemic therapy.
- Female: Pregnant or breastfeeding
- Expecting to conceive or father children within the projected duration of the trial, starting with the pre-screening or screening visit through 120 days after the last dose of trial treatment

Investigational Product Dosage and Administration

- Pembrolizumab 200 mg IV on Day 1 of each cycle.
- Pralatrexate 15, 20, or 30 mg/m² (according to dose level) on Days 1 and 8 of each cycle.
- 1 cycle = 21 Days.

Clinical Observations and Tests to be Performed

- Medical history and physical exam
- Safety assessments (CBCs with differential, comprehensive chemistry panel, thyroid function and coagulation)
- PET-CT
- CT/ MRI scans
- Correlative tumor tissue and blood samples.

TABLE OF CONTENTS

SECTION	PAGE
Protocol Team	2
Experimental Design Schema	3
Protocol Synopsis.....	4
Table of Contents	10
List of Tables and Figures.....	12
Abbreviations.....	13
1.0 Objectives.....	14
1.1 Primary Objectives.....	14
1.2 Secondary Objectives	14
1.3 Exploratory Objectives.....	14
2.0 Background.....	14
2.1 Introduction/Rationale for Development.....	14
2.2 Pembrolizumab.....	16
2.3 Pralatrexate	17
2.4 Leucovorin	18
2.5 Overview and Rationale of Study Design.....	18
3.0 Eligibility Criteria	20
3.1 Inclusion Criteria.....	20
3.2 Exclusion Criteria	22
4.0 Participant Enrollment	25
4.1 Pre-Enrollment Informed Consent and Screening Procedures.....	25
4.2 Participant Enrollment.....	25
4.3 Screen Failures and Registered Participants Who Do Not begin Study Treatment	26
4.4 Dose Level Assignment	26
5.0 Treatment Program	26
5.1 Study Overview.....	26
5.2 Treatment Cycle Definition.....	27
5.3 Treatment Plan	27
5.4 Eligibility criteria for initiation of subsequent treatment cycles	28

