3.2 Exclusion Criteria

Nature of Illness and Disease Status Criteria

- 1.** Patients with adult T-cell leukemia/lymphoma

Prior Therapy and Concomitant Therapy

- 2.** Prior allogeneic hematopoietic stem cell transplantation within the last 5 years.
- 3.** Prior autologous hematopoietic stem cell transplant within the last 60 days.
- 4.** Patients who received prior therapy with an anti-PD-1, anti-PD-L1, or anti-PD-L2 agent without having had evidence of objective response.
- 5.** Patients who received prior therapy with pralatrexate without having had evidence of objective response.
- 6.** Investigational agent or anti-cancer monoclonal antibody (mAb) within 21 days prior to Day 1 of therapy or who has not recovered (i.e. ≤ 1 or at baseline) from adverse events due to agents administered more than 21 days earlier.
- 7.** Prior chemotherapy, targeted small molecule therapy, or radiation therapy within 14 days prior to Day 1 of therapy or who has not recovered (i.e. ≤ 1 or at baseline) from adverse events due to a previously administered agent. Note: Subjects with \leq Grade 2 neuropathy are an exception and may qualify for the study.
- 8.** Antineoplastic biologic therapy or major surgery within 21 days of the first dose of trial medication. If subjects received major surgery more than 21 days ago, they must have recovered adequately from the toxicity and/or complications from the intervention prior to starting therapy.
- 9.** Received live vaccine or live-attenuated vaccine within 30 days prior to Day 1 of protocol therapy. Administration of killed vaccines is allowed.
- 10.** Systemic steroid therapy or on any other form of immunosuppressive therapy within 7 days prior to the first dose of trial treatment.

Participant MRN (COH Only):	Participant Initials (F, M, L):
Institution:	

Other Illnesses and Conditions

- 11. Diagnosis of immunodeficiency.
- 12. Has a known additional malignancy that is progressing or requires active treatment. Exceptions include basal cell carcinoma of the skin or squamous cell carcinoma of the skin that has undergone potentially curative therapy or in situ cervical cancer.
- 13. Congestive heart failure Class III/IV according to the New York Heart Association (NYHA) Functional Classification.
- 14. Known severe hypersensitivity reaction to pembrolizumab, pralatrexate, leucovorin or any excipients.

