- 15. Active autoimmune disease that has required systemic treatment in the past 2 years (replacement therapies for hormone deficiencies are allowed). Hemolytic anemia associated with the lymphoma does not exclude a patient from the study.
- 16. Known history of HIV (HIV ½ antibodies).
- 17. Known active Hepatitis B (e.g., HBsAg reactive) or Hepatitis C (e.g., HCV RNA [qualitative] is detected).
- 18. History of active TB infection (Bacillus Tuberculosis).
- 19. Active central nervous system (CNS) involvement by lymphoma, including parenchymal and/or lymphomatous meningitis. Subjects with prior CNS involvement by lymphoma must have a baseline MRI and lumbar puncture at screening that demonstrate no active lymphoma in the CNS.
- 20. Has a history of (non-infectious) pneumonitis/interstitial lung disease that required steroids or current pneumonitis/interstitial lung disease.
- 21. Active, uncontrolled infection requiring systemic therapy.
- 22. Female: Pregnant or breastfeeding
- 23. Expecting to conceive or father children within the projected duration of the trial, starting with the pre-screening or screening visit through 120 days after the last dose of trial treatment
- 24. Has known psychiatric or substance abuse disorders that would interfere with cooperation with the requirements of the trial.
- 25. History or current evidence of any condition, therapy, or laboratory abnormality that might confound the results of the trial, interfere with the subject's participation for the full duration of the trial, or is not in the best interest of the subject to participate, in the opinion of the treating investigator.
- 26. Any other condition that would, in the Investigator's judgment, contraindicate the patient's participation in the clinical study due to safety concerns with clinical study procedures.

Participant MRN (COH Only):

Participant Initials (F, M, L):

Institution:

Noncompliance

27. Prospective participants who, in the opinion of the investigator, may not be able to comply with all study procedures (including compliance issues related to feasibility/logistics).

Eligibility Confirmed* by (Choose as applicable):	Print Name	Signature	Date
 Site PI			
 Authorized study MD			
 Study Nurse			
 Study CRA/ CRC			
 Other: _____			

*Eligibility should be confirmed per institutional policies.

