5.4 Eligibility criteria for initiation of subsequent treatment cycles

Prior to initiation of Cycle 2 or any subsequent cycle, and based on the dose delay/modification guidelines provided in [Section 6.3](#) and [Section 6.4](#), patients will need to meet the following eligibility criteria:

- Mucositis \leq grade 1
- Platelet count \geq 25,000/ μ L
- ANC between 500-1,000/ μ L with no fever, or ANC \geq 1000/ μ L
- AST and ALT \leq 3 ULN OR \leq 5 ULN for subjects with hepatic involvement by lymphoma as the etiology of transaminase elevation
- Total serum bilirubin \leq 1.5 ULN OR Direct bilirubin \leq ULN for subjects with total bilirubin levels $>$ 1.5 ULN, unless has Gilbert's disease or hepatic involvement by lymphoma.
- No ongoing \geq grade 3 pralatrexate-related toxicity
- No \geq grade 2 pneumonitis, diarrhea/colitis, hypophysitis, nephritis/renal dysfunction, or intolerable/persistent immune-related AE
- No \geq grade 3 hyperthyroidism
- No evidence of myocarditis or newly onset type I diabetes mellitus
- No \geq grade 3 hyperglycemia associated with evidence of β -cell failure

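### Exclusion 4 admits prior PD-1/PD-L1/PD-L2 responders with no toxicity condition, so a resolved event that Table 6.3 treats as a permanent stop is, except for steroid-treated pneumonitis, left to investigator opinion

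*Combined protocol and SAP*

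**What the plan says.** Exclusion 4 of Section 3.2, repeated in the synopsis, bars "Patients who received prior therapy with an anti-PD-1, anti-PD-L1, or anti-PD-L2 agent without having had evidence of objective response". It asks only whether the earlier agent worked. It does not ask why that agent was stopped or what harm it did.

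Other entry criteria bear on earlier toxicity:

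- Exclusion 6 covers prior investigational agents and anti-cancer antibodies. It bars anyone "who has not recovered (i.e. ≤ 1 or at baseline) from adverse events due to agents administered more than 21 days earlier". Exclusion 7 applies the same recovery test to chemotherapy, small molecules and radiation.
- Exclusion 10 bars systemic steroids or other immunosuppression in the 7 days before the first dose.
- Inclusions 11 to 14 set limits on current bilirubin, AST, ALT and creatinine clearance. Exclusion 13 bars NYHA class III/IV heart failure.
- Exclusion 15 bars "Active autoimmune disease that has required systemic treatment in the past 2 years".
- Exclusion 20 works on history: "Has a history of (non-infectious) pneumonitis/interstitial lung disease that required steroids or current pneumonitis/interstitial lung disease".
- Exclusion 25 opens with "History or current evidence of any condition, therapy, or laboratory abnormality that might confound the results of the trial" and ends with a patient for whom it "is not in the best interest of the subject to participate, in the opinion of the treating investigator". Exclusion 26 is a further judgement clause.

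On study, Table 6.3 permanently stops pembrolizumab for listed immune-related events. Its general instruction 2 allows resumption after recovery to grade 0 or 1 only where pembrolizumab was withheld.

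**The concern.** The protocol treats the same history in two ways. If a patient has, say, grade 3 myocarditis on this trial, pembrolizumab is finished for that patient, and recovery does not reopen it. If the same event occurred earlier on another PD-1 inhibitor to which the patient responded, and it has since recovered, every specific entry criterion can be met. Whether the patient is re-exposed then depends on one investigator's view.

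What is at stake is patient safety. The dose holds in Table 6.3 and the accrual halts in Section 12.3.4 act only after re-exposure has happened. Exclusion 20 shows that the sponsor already accepts a past immune-type event as an entry bar, but for one organ only.

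**Working it through.** **Step 1. Set the permanent-stop rows beside the entry criteria.** The question for each row is whether any objective criterion bars a patient whose event has resolved.

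| Table 6.3 row | Pembrolizumab permanently stopped at | Objective bar on a resolved event |
|---|---|---|
| Pneumonitis | Grade 3–4, or recurrent grade 2 | Yes, exclusion 20 if steroids were needed |
| Diarrhea/colitis | Grade 4, or recurrent grade 3 | None |
| AST/ALT or bilirubin | Grade 3–4 | None (inclusions 11–13 test current values) |
| Nephritis/renal | Grade 3–4 | None (inclusion 14 tests current clearance) |
| Neurological | Grade 3–4 | None |
| Myocarditis | Grade 2–4 | None (exclusion 13 tests heart failure class) |
| SJS, TEN or DRESS | Confirmed | None |
| Other immune-related | Grade 4, or recurrent grade 3; grade 3 encephalitis and other clinically important events | None |

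The count is eight rows, one with a history bar and seven without.

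**Step 2. Check what the general criteria do.** Exclusions 6 and 7 catch an event that is still above grade 1 or baseline, and exclusion 10 catches a patient still on steroids. Unresolved events are therefore screened by rule. A patient who has recovered and finished steroids passes all three. Exclusion 15 requires active disease and does not say whether a drug-induced event counts. If it is read to include such events, it could catch some patients treated systemically within two years. Exclusion 14 ("Known severe hypersensitivity reaction to pembrolizumab, pralatrexate, leucovorin or any excipients") concerns hypersensitivity to the named drugs and reaches none of these rows. That leaves exclusions 25 and 26.

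**Step 3. Size.** The plan states no figure for how many such patients it expects. The inputs are:

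- Event frequency: Section 6.1.1 gives bands for pembrolizumab. Myocarditis, hepatitis, nephritis, encephalitis, Guillain-Barré syndrome, SJS and TEN are all marked below 1%. Colitis and raised AST/ALT are 1–10%, and diarrhea is at least 10%. No band is limited by grade, whereas Table 6.3 stops pembrolizumab for these last three only at the severe or recurrent grades shown above.
- Share of enrolled patients who are prior responders to this class: not given. Assumed 5% to 20%.
- Numbers: 30 evaluable patients expected, 40 maximum (Section 12.2).

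For myocarditis, share f = (prior responders) × (event frequency):

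- Low: 0.05 × 0.01 = 0.0005, so f is below 0.05%.
- High: 0.20 × 0.01 = 0.002, so f is below 0.2%.

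Chance of at least one such patient = 1 − (1 − f)^n:

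- n = 30: 1 − 0.9995^30 = 0.015 and 1 − 0.998^30 = 0.058.
- n = 40: 1 − 0.9995^40 = 0.020 and 1 − 0.998^40 = 0.077.

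These are upper bounds given the assumed responder share, because the band is itself an upper bound and covers all grades. A total over all eight rows cannot be computed, since the documents give no frequency by grade.

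**The case against.** The strongest reply is that entry is not unguarded. Exclusion 25 covers history and prior therapy and ends with the patient's best interest, and a competent investigator would not re-challenge after severe myocarditis. Table 6.3 itself leaves some decisions to judgement, for example in grade 3 events of the residual category and in grade 3–4 hypophysitis or hyperthyroidism. The patient in question is also rare.

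Most of this stands. It makes the gap one of reliance on discretion rather than absence of cover, and it limits the weight of the point. It does not remove the inconsistency, because for the rows in the table above Table 6.3 mandates the stop. An objective line also has a practical use: under Section 4.2.2 the completed Section 3 checklist goes to the Data Coordinating Center before registration, so a specific criterion can be checked centrally, whereas an opinion clause depends on each site.

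A reader might infer that Section 5.4 strengthens the case, because before cycle 2 and every later cycle it requires "No evidence of myocarditis or newly onset type I diabetes mellitus" and Section 3 has no matching line for cycle 1. It does not. That line tests current state, and a patient with resolved myocarditis would satisfy it. The contrast rests on Table 6.3 alone.

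**Conclusion.** The point holds for resolved events. Apart from steroid-treated pneumonitis, no objective criterion bars a prior responder with a recovered event that Table 6.3 treats as a permanent stop, unless exclusion 15 is read to include drug-induced events.

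Three stronger readings are not supported:

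- A reader might infer that immune toxicity from earlier checkpoint therapy is screened only by opinion. Unresolved toxicity is screened by rule.
- A reader might infer that such a patient is likely to enrol. Assuming 20% prior responders and a stop event in 20% of them gives a 4% share, hence 1 − 0.96^30 = 71% in 30 and 1 − 0.96^40 = 80% in 40. Nothing in Section 6.1.1 supports 20% for stop-grade events. Most of the types concerned are below 1%, and the bands of 10% or more are for any-grade diarrhea, nausea, fatigue, pruritus and rash.
- A reader might infer that the MTD is at risk. No such effect is claimed. With an assumed 15% background DLT risk and 50% in such a patient, a 0.25% share moves the probability of at least 2 DLTs in 6 only from 22.4% to 22.6%.

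For myocarditis, the chance of at least one such patient is below about 1.5–5.8% in 30 and 2.0–7.7% in 40. This rests on the assumed 5–20% responder share, and on bands from general pembrolizumab use, which are only a guide for patients previously treated with other agents of the class. The change is a cheap improvement, justified by the severity of a preventable re-exposure rather than by its frequency.

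**What to change.** In exclusion 4, in both Section 3.2 and the synopsis, add:

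*or who permanently discontinued such an agent because of an immune-related adverse event, or had on it an immune-related event of a type and grade for which Table 6.3 mandates permanent discontinuation of pembrolizumab (including grade 3 encephalitis or other clinically important irAEs), except endocrinopathy controlled by hormone replacement or type 1 diabetes under metabolic control.*

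The first limb can be answered from the treatment history, without regrading an event managed elsewhere. The second ties entry to the protocol's own table. The exception follows the note under Table 6.3, which allows pembrolizumab to resume in controlled endocrinopathy. Exclusion 5 (prior pralatrexate) needs no change.

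The cost is one clause in two places. The downside is that a few previously treated patients no longer qualify.
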